#### 8.2.2. Secondary endpoints

Secondary endpoints will include:

- Hematological responses at 3 months (as defined above)
- Time to response
- Best response, regardless of response status at primary endpoint
- Impact on platelet count and neutrophil count
- Relapse during the extension phase
- Clonal evolution, according to cytogenetic, mutational or flow cytometric markers
- Toxicities with extended duration of therapy
- The impact of treatment and treatment response on quality of life.
- Evaluation of neurodevelopmental changes at baseline and 6-month evaluations.
- Iron loading as measured by ferritin trends at each evaluation, and by iron staining of bone marrow biopsies at baseline and 6-month evaluations (and during extension at the PI's discretion)
- Evaluation of reactive oxygen species HSPCs (ROS flow cytometry assay at baseline and 6 months), and at interval evaluations during extended access at the PI's discretion

- Evaluation of global transcriptome in HSPCs (single cell RNA seq at baseline and 6 months)
- The impact of eltrombopag on reconstitution of the stem cell compartment (multicolor flow cytometry of bone marrow cells) and erythroid compartment (multicolor flow cytometry and CFU-E/BFU-E assays) at baseline and 6-month evaluations, and at interval evaluations during extended access at the PI's discretion

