Our own experiences with EPAG have confirmed that it is a potent chelator of iron and can mobilize whole body iron stores even in transfusionally iron-overloaded patients (61). Specifically, in patients on EPAG for at least 4 months, whole body iron as measured by serum ferritin was decreased, especially in patients treated on an extended access protocol (Figure 2), including our index DBA patient (Figure 1D). Paradoxically, in patients being treated with EPAG, serum iron levels are actually elevated, reflecting the mobilization of the intracellular iron into the blood stream, from which it is ultimately cleared and lost via hepatic processing of the iron-bound drug. Indeed, in several patients treated on extended doses of EPAG (average 2 years of drug exposure), iron supplementation was required due to the development of iron deficiency anemia in the face of an otherwise strong response to EPAG. Several investigations into the metabolic effects of EPAG in cells have demonstrated that through the depletion of iron, there is a concomitant reduction in the toxic reactive oxygen species (59, 63, 72, 73).

**Figure 2: Impact of eltrombopag upon iron stores in patients treated for aplastic anemia.** (A) Ferritin levels in patients with EPAG treatment for at least 4 months. (B) Comparison of ferritin levels pretreatment and after EPAG discontinuation in 6 patients with prolonged EPAG treatment and ferritin measurements available at follow-up. Student's *t* test: \*\**P* = .005 (61)

Given these findings of intracellular iron depletion, improvement in reactive oxygen species levels, and the clinical response we have previously seen in our DBA patient, we hypothesize that through its iron chelating properties, likely in combination with its stimulatory effects upon TPOR, EPAG may be able to offset the toxic effects of aberrant hemoglobin biosynthesis in DBA patients, increasing erythroid production, and ultimately allowing HSC self-renewal, thus improving anemia, preventing the long-term hematologic consequences of DBA, and even avoid the significant toxicities of transplant. By chelating and subsequently removing total body iron effectively, we hypothesize that EPAG will also improve organ function and overall long-term outcomes in DBA patients previously experiencing iron overload as a consequence of prior transfusion therapy.

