# 3. Study Design

The study is designed as a single-site, non-randomized, single-arm pilot study of the oral TPOR agonist eltrombopag (EPAG) in Diamond-Blackfan anemia (Figure 3) to test the hypothesis: *eltrombopag improves the production of red blood cells in Diamond-Blackfan anemia patients.* The primary endpoint (see §8.2) is measured at 6 months (24 weeks ± 14 days). Subjects who cannot tolerate the medication or fail to respond by the primary endpoint will be taken off study drug. Subjects who *respond* at the primary endpoint (hemoglobin increase of 1.5 g/dL or more and/or transfusion independence for the previous 8 weeks, see §8.2.1) will be able to continue EPAG on the extension part of this protocol for an additional 3 years. During the 3-year extension phase, subjects will remain on the same dose of EPAG until they reach a *robust response* (defined as hemoglobin ≥10 g/dL in the absence of transfusions for more than 8 weeks, see §8.2.1). Drug dose will then be tapered slowly to the lowest dosage that maintains a stable hemoglobin (≥ 10 g/dL) and eventually discontinued if possible (per §5.3), until they meet off study criteria (see §8.6), or the study is closed. Drug will be restarted during extension if robust response is lost (*i.e.* hemoglobin falls below 9 g/dL).

Up to 30 subjects (18 for Stage 1 & 12 for Stage 2) will be screened to accrue 25 eligible subjects for this study.

[figure not shown]

Figure 3: Study enrollment and treatment schema

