# Table 2: Criteria for the adjustment of the daily dose of eltrombopag

## 5.3. Taper of eltrombopag in the extension protocol

Once a robust blood count recovery occurs in the extension part (*i.e.* hemoglobin >10 g/dL in the absence of transfusions for more than 8 weeks), EPAG dose will be tapered according to Table 3. If hemoglobin falls to <9 g/dL or the patient again requires RBC transfusions then EPAG will be either re-initiated or the dose will be increased to the last effective strength.

Age group	Starting dose	Step 1	Step 2	Step3	Step 4
		Non-Asia	an		
≥12	150 mg	75	37.5	25	stop
6-11	75 mg	37.5	25	12.5	stop
2-5	2.5 mg/kg	1.25mg/kg	stop		
East Asian, South East Asian					
≥12	75 mg	37.5	25	12.5	stop
6-11	37.5 mg	25	12.5	stop	
2-5	1.25 mg/kg	stop			

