## 5.7. Permitted supportive care

- Transfusion supportive care (e.g., blood and platelets) as clinically indicated.
- Iron chelation therapy (e.g. deferasirox, deferoxamine, deferiprone) ongoing at the time of enrollment will be continued, titrating and/or discontinuing according to established standards of care.
- Estrogens or combination oral contraceptives as indicated for uterine bleeding.
- Prophylactic antibiotics and antivirals as clinically indicated.
- The PI should be informed about all medications initiated after starting treatment with EPAG.

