#### Table 8: Attribution of adverse events

Relationship	Attribution	Description
Unrelated to investigational	Unrelated	The AE is clearly NOT related to the intervention
agent/intervention 	Unlikely	The AE is doubtfully related to the intervention
Related to investigational agent/intervention 	Possibly	The AE may be related to the intervention
	Probably	The AE is likely related to the intervention
	Definitely	The AE is clearly related to the intervention

**NOTE:** AEs listed as 'possibly, probably, or definitely' related to the investigational agent/intervention are considered to have a suspected 'reasonable causal relationship' to the investigational agent/intervention (ICH E2A).

In view of the underlying disease (Diamond-Blackfan anemia), all patients will enter the study with abnormally low blood counts that would meet criteria for grade 2 and more commonly higher toxicity. Also, platelet and red blood cell counts will be impacted by frequent transfusions. Therefore, AEs regarding low hematologic lab values, including thrombocytopenia or platelet-transfusion dependence, anemia or red cell transfusion dependence, neutropenia, lymphopenia, or leukopenia are not evaluable and will not be recorded.

Non-hematologic abnormal laboratory findings used to evaluate the safety of this protocol regimen will include any change from laboratory assessments done prior to first dose of study medication that result in a progression to grade 3 or 4 laboratory toxicity or are characterized by any of the following:

- Results in discontinuation from the study
- Is associated with clinical signs or symptoms
- Requires treatment or any other therapeutic intervention
- Is associated with death or another serious adverse event, including hospitalization
- Is judged by the Investigator to be of significant clinical impact
- If any abnormal laboratory result is considered clinically significant, the investigator will provide details about the action taken with respect to the test drug and about the patient's outcome.

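### Iron deficiency anemia on long-term eltrombopag, which the protocol itself reports, has no adverse-event rule or low-side endpoint and could be missing from the extended-toxicity results.

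*Combined protocol and SAP*

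**What the plan says.** **The harm.** Section 2.4.2 describes patients on extended eltrombopag, with about 2 years of exposure on average, in whom "iron supplementation was required due to the development of iron deficiency anemia in the face of an otherwise strong response to EPAG". It gives no rate or denominator, and the observation is not specific to Diamond-Blackfan anemia. The same section says serum iron is raised on the drug while stores fall.

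**The iron endpoint.** Section 8.2.2 lists "Iron loading as measured by ferritin trends at each evaluation, and by iron staining of bone marrow biopsies at baseline and 6-month evaluations". No lower threshold or deficiency category is given, and section 8.4 names no analysis of iron data. Toxicity of extended therapy and relapse in the extension are separate secondary endpoints in the same list. Relapse is not defined.

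**The recording rule.** Section 9.2.2 (text after Table 8) says that events of low hematologic values, including "anemia or red cell transfusion dependence, neutropenia, lymphopenia, or leukopenia are not evaluable and will not be recorded". There is no exception by cause. The reasons given are low counts at entry and frequent transfusion.

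**The extension.** Responders may continue for 3 more years (section 6.5). Section 3 says "Drug will be restarted during extension if robust response is lost", meaning hemoglobin below 9 g/dL. Section 5.3 says "If hemoglobin falls to <9 g/dL or the patient again requires RBC transfusions then EPAG will be either re-initiated", or else the dose goes back up to the last effective strength. Neither section refers to iron status. Under section 5.7, other iron chelation "ongoing at the time of enrollment will be continued"; that sentence goes on to allow titration or discontinuation by standard of care.

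**The concern.** Three rules meet on one event, and none of them provides for it. A responder who has become transfusion-free and then turns anemic from iron depletion shows falling ferritin, falling hemoglobin and no recordable anemia event. The reasons given in section 9.2.2 for not recording anemia do not fit this subject, who is no longer transfused and whose anemia is new.

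Two secondary endpoints are at stake. The extended-toxicity summary could omit a drug effect the investigators have already seen. The relapse figure could include hemoglobin falls that are due to iron depletion and not to loss of drug effect. The eltrombopag risk text and expected-event tables in section 10.3.1 do not name iron deficiency (anemia appears only as an expected event in severe aplastic anemia), so they do not prompt anyone to look for it.

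**Working it through.** **1. Can the exposure be reached?** Longest planned exposure is 24 weeks plus 3 years: 24/52 + 3 = 3.46 years, which exceeds the 2-year average in section 2.4.2. Not everyone gets there. By Table 3, a subject aged 12 or over who starts the taper straight after 6 months has three 8-week dose steps before stopping: 24 + 3 × 8 = 48 weeks. The exposure at issue therefore falls mainly on responders who do not reach the robust level and on those restarted.

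**2. How many subjects?** Section 8.3 gives a Simon minimax design: at least 2 responders of 15 to continue, at least 6 of 25 to reject, null rate 10%, alternative 30%, significance level 0.05, power 0.80. An exact two-stage binomial calculation gives a type I error of 0.0328 and power of 0.8017, so the stated design reproduces. If all 25 are enrolled and every responder enters the extension:
- fewest responders that reject the null: 6
- expected under the alternative: 0.30 × 25 = 7.5, rounded to 8

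**3. Effect of one misclassified case on the relapse proportion.** 1/8 = 12.5 points; 1/6 = 16.7 points.

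**4. Chance of at least one case.** With per-subject rate q and m extension subjects, this is 1 − (1 − q)^m. The documents give no q, so these rates are assumptions:

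| Assumed q | m = 6 | m = 8 |
|---|---|---|
| 5% | 26% | 34% |
| 10% | 47% | 57% |
| 20% | 74% | 83% |
| 30% | 88% | 94% |

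**5. Where would a case be recorded?**
- As anemia: nowhere, because section 9.2.2 excludes it.
- As a laboratory event: possibly. Section 9.2.2 counts non-hematologic laboratory changes that need treatment, cause symptoms or are judged clinically important. Whether ferritin is non-hematologic is not stated. An unrecognised or untreated case may meet none of these conditions.
- In the iron endpoint: as part of a ferritin trend, with nothing to separate unloading from deficiency.
- In the relapse endpoint: unknown, because relapse is undefined. The nearest operational rules (sections 3 and 5.3) use hemoglobin and transfusion only.

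**6. Are the data there?** Yes. On drug, ferritin is drawn every 4 weeks and a full iron panel every 6 months (sections 6.5 and 6.5.1). After discontinuation for robust response, ferritin is monthly for 6 months and then every 3 months (section 6.5.2).

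**The case against.** A reader might infer that the plan will report iron deficiency only as a benefit or as relapse. The documents do not support that.
- Extended toxicity is its own endpoint, and the cases in section 2.4.2 were treated, so cases like them could qualify as laboratory events needing intervention.
- A trend covers both directions, and no mean-ferritin analysis is planned.
- No text scores these falls as relapse. The 9 g/dL rule governs loss of robust response and restart of drug.
- Section 10.2 treats chelation as a possible harm, since it is the reason for neurodevelopmental testing in children.
- Section 5.7 lets other chelators be titrated or stopped.
- Section 2.4.2 does not say that hemoglobin fell below 9 g/dL in the reported cases.
- This is a single-arm pilot with no specified test on relapse, and cases could be found from the ferritin data at reporting.

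All of that stands, and it limits the point to what could happen. It does not remove the anemia exclusion, which makes no exception by cause, or settle whether ferritin falls under the laboratory route. Finding cases after the fact also needs a rule, and none is written.

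**Conclusion.** The concern holds as a risk of omission and misclassification. The protocol reports the harm, excludes anemia of every cause from recording, and defines its only iron endpoint without a low side. A drug-induced iron deficiency anemia in the extension could therefore be absent from the extended-toxicity results, particularly if unrecognised or untreated, and could be taken for falling iron load or loss of response.

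Each misclassified case would move the relapse proportion by about 12 to 17 points. That rests on 6 to 8 subjects entering the extension and on such a fall being counted as relapse, which the plan leaves open. The number of cases is an assumption. The 6-month primary endpoint is little affected, because the reported harm arose at about 2 years on average.

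**What to change.** 1. **Section 9.2.2:** exempt new iron deficiency anemia from the bar on recording anemia, and state whether ferritin and other iron measures count as non-hematologic laboratory findings.
2. **Sections 8.2.2 and 8.4:** under the extended-toxicity endpoint, report the number of subjects with ferritin below the laboratory's lower limit at any scheduled draw. Ferritin should lead. Transferrin saturation is supportive only, because serum iron rises on the drug and may mask depletion. Describe the count as a lower bound, since inflammation raises ferritin.
3. **Section 8.2.2:** define relapse. Report it for all hemoglobin falls as the main figure, and flag descriptively those with low ferritin at the nearest scheduled draw. Dropping them from the main figure would remove a drug-caused failure and could flatter efficacy.
4. **Sections 5.3 and 2.4.2:** the sponsor must reconcile a rule that acts on hemoglobin and transfusion alone with the harm reported for the same drug. No clinical rule is proposed here.

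The cost is wording and two short summaries from data already collected, with no new visits or tests. The remaining limit is timing: once ferritin is 3-monthly off drug, the nearest draw may be some weeks from the hemoglobin fall.

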#### 8.3. Sample size

Because the efficacy of eltrombopag in this patient population is unknown, we would like to reject the treatment as quickly as possible with a small number of patients if the treatment is not effective. We will use the Two-Stage Minimax Design outlined in Table 1 of Simon (89) with a response probability of 10% or less to terminate the treatment and the hypothesized actual response probability of 30% or more. The sample size is determined by testing the null hypothesis  $H_0$ :  $p \le 10\%$  versus the alternative  $H_1$ :  $p \ge 30\%$  at a significance level of 0.05 and a power of 0.8. At the first stage, we will accrue 15 subjects, and the null hypothesis will be accepted if no more than 1 subject responds to the treatment at 6 months. If 2 or more subjects respond to the treatment at 6 months at the first stage, then we will accrue an additional 10 subjects, bringing the total number of subjects to n = 25. The null hypothesis of  $p \le 10\%$  will be accepted if the total number of responders at 6 months is 5 or less. These efficacy thresholds were selected as being clinically relevant for the avoidance of alternative therapies such as hematopoietic stem cell transplant. Given an observed screening fail rate of 16.7%, we will recruit 30 patients (18 in the first phase, 12 in the second phase) to ensure that the target of 25 eligible patients is reached.

With an incidence of approximately 1 in 100,000-200,000 live births (18), and an expectation of approximately 25-35 new diagnoses a year in the USA, of which 15-20 will likely prove refractory to treatment, and in conjunction with recruitment through patient networks and ongoing natural history studies at the NIH (see §10.1), accrual is projected to take 2.5-3 years.

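### Capping screening at 30 makes 25 eligible subjects the expected number, not an assured one, so the stated sample size and 80% power are not secured

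*Combined protocol and SAP*

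**What the plan says.** Section 8.3 adopts a published two-stage design: "We will use the Two-Stage Minimax Design outlined in Table 1 of Simon". The null response rate is 10%, the alternative is 30%, and the test is set "at a significance level of 0.05 and a power of 0.8". On stage 1 it says: "At the first stage, we will accrue 15 subjects, and the null hypothesis will be accepted if no more than 1 subject responds". With 2 or more responders, "then we will accrue an additional 10 subjects, bringing the total number of subjects to n = 25", and the null is accepted at the end with 5 or fewer responders.

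The same section then uses an observed screen-failure rate of 16.7% to set recruitment at 30, as 18 in the first stage and 12 in the second, "to ensure that the target of 25 eligible patients is reached". Section 3 turns that figure into a limit: "Up to 30 subjects (18 for Stage 1 & 12 for Stage 2) will be screened to accrue 25 eligible subjects".

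I found no provision for screening beyond 30 if more subjects fail, and no decision rule for a stage that ends short of its number.

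**The concern.** Dividing the target by the expected pass rate gives the number screened at which the mean number eligible equals the target. It leaves no margin for chance. When that number is also a ceiling, a run of failures slightly worse than average cannot be made up, and a shortfall becomes a common outcome.

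This matters more here than in many designs because the minimax design only just reaches its power. The boundaries of 1 in 15 and 5 in 25 were chosen for exactly those sample sizes. If fewer than 25 subjects are enrolled, the stated power no longer holds. The team would also have to choose a final cut-off that the protocol does not supply, possibly after seeing the responses.

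**Working it through.** **Inputs.** From section 8.3: p0 = 0.10, p1 = 0.30, first-stage rule 1/15, final rule 5/25, screen-failure rate d = 16.7% (taken as 0.167 or 1/6). From sections 8.3 and 3: 30 screened, split 18 + 12, as an upper limit. My assumptions: each subject is one independent final pass or fail, with constant d.

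**1. The design reproduces.** The probability of rejecting the null is the sum over x = 2 to 15 of P(X1 = x) × P(X2 ≥ 6 − x), where X1 ~ Bin(15, p) and X2 ~ Bin(10, p).
- At p = 0.10: 0.0328, within the 0.05 bound.
- At p = 0.30: 0.8017, which clears 0.80 by less than 0.2 percentage points.

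A search over two-stage designs confirms that 25 is the smallest total meeting both limits, and that 1/15, 5/25 has the smallest expected sample size under the null at that total.

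**2. The screening number reproduces.** 25/(5/6) = 30, 15/(5/6) = 18 and 10/(5/6) = 12. With d = 0.167, 25/0.833 = 30.01.

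**3. What 30 delivers.** The expected number eligible is 30 × 5/6 = 25. The chance of reaching 25 is P(Bin(30, 1 − d) ≥ 25):

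| True final failure rate | P(at least 25 of 30) |
|---|---|
| 10% | 0.93 |
| 16.7% | 0.615 (0.616 at exactly 1/6) |
| 20% | 0.43 |
| 25% | 0.20 |

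At 16.7% a shortfall therefore occurs about 38% of the time, and 23 or fewer are eligible about 22% of the time. For stage 1 taken alone, P(at least 15 of 18) = 0.648.

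**4. What a shortfall does to the test.** Keep stage 1 at 1/15 and the final cut-off at 5, and let the total n fall:

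| Total n | Power at 30% | Type I error at 10% |
|---|---|---|
| 25 | 0.802 | 0.033 |
| 24 | 0.768 | 0.027 |
| 23 | 0.729 | 0.022 |
| 22 | 0.686 | 0.018 |

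Average over the eligible count with a pooled cap of 30, that is, the sum over x of P(Bin(30, 0.833) = x) × power at n = min(25, x). Power is 0.771 and type I error 0.029.

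**5. Lowering the final cut-off does not repair it.** With the cut-off at 4 and the same stage 1, type I error is 0.082 at n = 24, 0.071 at n = 23 and 0.061 at n = 22. All exceed 0.05.

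**6. Ceiling needed at 16.7%.** P(at least 25 eligible) is 0.85 with 32 screened, 0.91 with 33 and 0.95 with 34.

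**The case against.** The strongest reply is that this is the ordinary inflation formula, correctly computed, and that the consequence is small. Both halves of that stand. Average power drops by about 3 points (0.802 to 0.771) in a single-arm pilot. Keeping the cut-off of 5 makes a short trial conservative. The binomial estimates and confidence intervals in section 8.4 work at any n. Under the null the trial stops after stage 1 with probability 0.55, and then 25 are never needed.

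A second reply is that 0.62 depends on the model. Section 4.2 lets subjects with modifiable findings be re-screened, and section 8.3 does not say whether 16.7% is counted before or after that. If before, the final failure rate is lower and the chance higher: 0.71 at 15%, 0.84 at 12.5%. No denominator is given for the observed rate. Section 6.1 also allows eligibility work under another protocol, so it is unclear which failures use one of the 30 places. These points make 0.62 conditional. They do not turn an average into an assurance.

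A third reply is that the team could amend the protocol and screen more. It could, but nothing in the text commits to that.

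A reader might also multiply the stage probabilities, 0.648 × 0.677 = 0.439, and conclude that the plan fails more often than not. The documents do not support that figure, because they do not say that unused stage 1 places cannot pass to stage 2.

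**Conclusion.** The point holds as a matter of wording and a missing contingency. The plan presents an expected count as an assured one and then makes it a ceiling. On the stated rate, with independent screenings and one final outcome per subject, the chance of reaching 25 is about 0.62. Because the design has almost no spare power, losing even one subject takes it below the stated 0.80. Averaged over a pooled cap of 30, power is about 0.77.

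Three stronger conclusions might be inferred, and none is supported. There is no arithmetic error in the step from 25 to 30. The type I error is not compromised as long as the cut-off of 5 is kept. The figure of 0.62 is not unconditional: it moves from 0.93 to 0.43 as the true final failure rate goes from 10% to 20%, and the documents do not show where in that range the rate lies.

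**What to change.** In section 8.3 and section 3, define accrual by the number enrolled: screen until 15 eligible subjects are enrolled in stage 1 and, if the trial continues, until 25 are enrolled in total, with about 30 screened expected. If a ceiling is needed, set it at about 33 to 34, which gives 91% to 95% at a failure rate of 16.7%. The assurance is lower if the true rate is higher: a ceiling of 34 gives 87% at 20%.

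If the limit of 30 has to stay, describe 25 as the expected number. Report the probability of about 62% and the average power of about 77%, with the assumptions behind them. State in advance that the 5-responder cut-off is kept if fewer than 25 are enrolled.

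The cost is a wording amendment and a few more screening evaluations. These are not trivial for the people concerned, since section 6.1 includes a bone marrow aspiration and biopsy and subjects may be as young as 2 years. The number treated stays at 25.
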